9 STATISTICAL CONSIDERATIONS

A description of statistical methods is provided below and will be described in more detail in the Statistical Analysis Plan (SAP).

9.1 Definition of analysis sets

The Enrolled Set (ES) will consist of all study participants who have given informed consent.

The Randomized Set (RS) will consist of all randomized study participants.

The Safety Set (SS) will consist of all study participants that received at least 1 dose of the IMP.

The Full Analysis Set (FAS) will consist of all randomized study participants that received at least 1 dose of the IMP and have a valid measurement of the co-primary efficacy variables at Baseline.

The Per-Protocol Set (PPS) will consist of all study participants in the RS who had no important protocol deviations affecting the co-primary efficacy variables. Important protocol deviations will be predefined, and study participants with important protocol deviations will be evaluated during ongoing data cleaning meetings prior to unblinding the data (see Section 9.5).

The Pharmacokinetics Per-Protocol Set (PK-PPS) will consist of all randomized study participants who received at least 1 dose of the IMP and provided at least 1 quantifiable plasma concentration postdose without important protocol deviations that would affect the concentration.

9.2 General statistical considerations

Summary statistics will consist of frequency tables for categorical variables. For continuous variables, summary statistics will consist of the number of available observations, arithmetic mean, standard deviation, median, minimum, and maximum, unless stated otherwise.

All analyses will be performed using SAS[®] version 9.3 or later (SAS Institute, Cary, NC, US).

The statistical analysis of the co-primary efficacy variables will be performed using a Type I error rate at a 2-sided alpha level of 0.05.

9.3 Planned efficacy/outcome analyses

Efficacy variables will be analyzed for all study participants in the RS.

9.3.1 Efficacy estimands

The following 4 attributes describe the estimands (International Council for Harmonisation [ICH] Addendum, 2019) that will be used to define the treatment effect of interest for the co-primary endpoints of study participant-level outcomes:

PASI90 response at Week 16:

1. Treatment: 320mg bimekizumab Q4W for 16 weeks.
2. Target Population: adult Korean study participants meeting the protocol-specified inclusion/exclusion criteria.
3. Intercurrent event handling: An intercurrent event is defined as discontinuation of IMP prior to Week 16. A composite strategy will be implemented in which a positive clinical outcome is defined as achieving PASI90 response at Week 16 and not discontinuing IMP through Week 16.
4. Study participant-level summary measure: Odds ratio comparing bimekizumab to placebo.

Any missing data not associated with discontinuation of IMP will also be imputed as a nonresponse.

IGA 0/1 (clear or almost clear with at least a 2-category improvement from Baseline) response at Week 16:

1. Treatment: 320mg bimekizumab Q4W for 16 weeks.

2. Target Population: adult Korean study participants meeting the protocol-specified inclusion/exclusion criteria.
3. Intercurrent event handling: An intercurrent event is defined as discontinuation of IMP prior to Week 16. A composite strategy will be implemented in which a positive clinical outcome is defined as achieving IGA 0/1 response at Week 16 and not discontinuing IMP through Week 16.
4. Study participant-level summary measure: Odds ratio comparing bimekizumab to placebo.

Any missing data not associated with discontinuation of IMP will also be imputed as a nonresponse.

The secondary efficacy binary endpoints (PASI100 response at Week 16, IGA 0 response at Week 16, PASI75 response at Week 4, PSD [P-SIM] [itch, pain, and scaling] response at Week 16, Scalp IGA 0/1 response at Week 16, and DLQI Total Score 0/1 response at Week 16) will have the same estimand structure as for the primary estimands.

The following 4 attributes describe the estimand (ICH Addendum, 2019) that will be used to define the treatment effect of interest for the secondary efficacy endpoint percentage change from Baseline in BSA affected by PSO Week 16:

1. Target population: Study participants meeting the protocol-defined inclusion/exclusion criteria.
2. Study participant-level outcome: Percentage change from Baseline in BSA affected by PSO at Week 16
3. Intercurrent event handling: A hypothetical strategy will be implemented in which the estimand targets the treatment difference in a scenario where an intercurrent event does not occur, such that outcomes for study participants without an intercurrent event are as observed, and outcomes for study participants with an intercurrent event are treated as though they had completed the randomized study treatment through Week 16 by imputing data following an intercurrent event using multiple imputation (MI).
4. Study participant-level summary measure: Difference in the adjusted means between bimekizumab and placebo.

Any missing data not associated with discontinuation of IMP will also be imputed using MI.

9.3.2 Analysis of the primary efficacy/primary endpoint

The co-primary efficacy variables for this study will be PASI90 response and IGA 0/1 response at Week 16.

The primary analyses for these endpoints will be produced on the RS. In addition, sensitivity analyses for the co-primary endpoints will be produced on the FAS and PPS. Observed case summaries (excluding subjects with missing PASI/IGA data at Week 16) will also be provided.

Estimands related to primary efficacy analyses are described in Section 9.3.1.

An intercurrent event is defined as discontinuation of IMP prior to Week 16. A composite strategy will be implemented in which a positive clinical outcome is defined as achieving the primary endpoint (PASI90 or IGA 0/1) at Week 16 and not discontinuing IMP prior to Week 16.

The justification of this approach is that discontinuation of IMP for any reason is considered to be indicative of an ineffective response to the IMP. Therefore, a successful primary outcome depends both on achieving the response (PASI90 or IGA 0/1) and continuing study treatment through 16 weeks.

A study participant will be classified as a PASI90 responder if the PASI score at Week 16 has improved at least 90% from Baseline and the study participant has not discontinued IMP prior to Week 16.

A study participant will be classified as a IGA 0/1 responder if the IGA score at Week 16 is 0 or 1 (clear or almost clear) with at least a 2-category improvement from Baseline in the IGA score and the study participant has not discontinued IMP prior to Week 16.

The evaluation of superiority (bimekizumab vs placebo treatment comparison) will be based on the Cochran-Mantel-Haenszel (CMH) test. Odds ratios and 95% confidence intervals (CIs) based on the CMH method will also be presented.

9.3.3 Secondary efficacy endpoint analyses

The secondary efficacy variables will be analyzed for all study participants in the RS.

No formal statistical testing will be conducted for the secondary efficacy variables. Nominal p-values for the bimekizumab vs placebo treatment comparison will be described in the SAP.

The secondary efficacy endpoints will be derived as follows:

- PASI100 responder at Week 16: PASI score at Week 16 has improved by 100% from Baseline and the study participant has not discontinued IMP prior to Week 16.
- IGA 0 responder at Week 16: IGA score at Week 16 is 0 (Clear) with at least a 2-category improvement from Baseline in the IGA score and the study participant has not discontinued IMP prior to Week 16.
- PASI75 responder at Week 4: PASI score at Week 4 has improved by $\geq 75\%$ from Baseline and the study participant has not discontinued IMP prior to Week 4.
- PSD (P-SIM) itch responder at Week 16: Itch score has improved (decreased) by ≥ 4 points from Baseline to Week 16 (using weekly averages) and the study participant has not discontinued IMP prior to Week 16. This will be assessed only in study participants with a Baseline itch score ≥ 4 .
- PSD (P-SIM) pain responder at Week 16: Pain score has improved (decreased) by ≥ 4 points from Baseline to Week 16 (using weekly averages) and the study participant has not discontinued IMP prior to Week 16. This will be assessed only in study participants with a Baseline pain score ≥ 4 .
- PSD (P-SIM) scaling responder at Week 16: Scaling score has improved (decreased) by ≥ 4 points from Baseline to Week 16 (using weekly averages) and the study participant has not discontinued IMP prior to Week 16. This will be assessed only in study participants with a Baseline scaling score ≥ 4 .
- Scalp IGA 0/1 responder at Week 16 for study participants with scalp involvement at Baseline: Scalp IGA score at Week 16 is 0/1 (clear or almost clear) with at least a 2-category

improvement from Baseline in the IGA score and the study participant has not discontinued IMP prior to Week 16. Only study participants with a Scalp IGA score ≥ 2 at Baseline will be included.

- DLQI Total Score 0/1 at Week 16: DLQI Total score is equal to 0 or 1 at Week 16 and the study participant has not discontinued IMP prior to Week 16.

For the binary secondary efficacy endpoints assessing the superiority of bimekizumab vs placebo, the estimand structure as specified for the primary analysis will be implemented.

For the continuous change from Baseline efficacy endpoint, percent change from Baseline in BSA affected by PSO at Week 16, an analysis of covariance (ANCOVA) model will be used with fixed effects of treatment and Baseline value as a covariate. Missing data will be imputed via MI as outlined in the estimand structure (Section 9.3.1). If there are model convergence issues with MI, a last observation carried forward (LOCF) approach will be used.

For all secondary efficacy endpoints, observed data summaries will also be presented.

9.3.4 Tertiary efficacy endpoint analyses

The tertiary efficacy variables will be analyzed for all study participants in the RS.

Binary (responder) variables will be summarized using frequency tables by treatment group for each visit; nonresponder imputation (NRI) and observed case results will be displayed.

Continuous variables will be summarized using descriptive statistics by treatment group for each visit. No imputation will be applied to continuous variables, only observed data will be summarized.

Time to PASI50, PASI75, PASI90, and PASI100 response will be estimated using the Kaplan-Meier product-limit method for each treatment group. Time to a given response will be defined as the length in days from the first dose of IMP until the first date when the response is achieved. Study participants who discontinue IMP prior to achieving a response will be censored at the date of the last observed PASI assessment on or prior to the date of IMP discontinuation. Study participants who complete the study without achieving the given response will be censored at the date of the last observed PASI assessment.

Study participants will be censored at Baseline (Day 0) if there is no Baseline PASI assessment or no post-Baseline PASI assessment.

The median time to response, including the 2-sided 95% CI, will be calculated for each treatment group.

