5.5.3 Time to PASI50/70/90/100 response

Time to PASI50, PASI75, PASI90, and PASI100 response (in days) during the Treatment Period will each be calculated as:

Date of first PASI xx response – Date of first study drug administration + 1.

with xx representing 50, 70, 90, 100 respectively. All visits including unscheduled visit are considered.

Time to PASI50, PASI75, PASI90, and PASI100 response will be estimated using the Kaplan-Meier product-limit method for each treatment group. Study participants who discontinue IMP prior to achieving a response will be censored at the date of the last observed PASI assessment on or prior to the date of IMP discontinuation. Study participants who complete the study without achieving the given response will be censored at the date of the last observed PASI assessment in the Treatment Period. Study participants will be censored at Baseline (Day 0) if there is no Baseline PASI assessment or no post-Baseline PASI assessment in the Treatment Period.

Kaplan-Meier plots of time to PASI responses will also be provided by treatment group. In these Kaplan-Meier plots, the line will start at 0 (since there are no responders at Week 0) and will increase over time, representing time to achieving the response.

The median time to response, including the 2-sided 95% CI, will be calculated for each treatment group.

Safety Analyses

Safety variables will be analyzed for all study participants in the SS.

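### Censoring participants who stop IMP before responding makes the time-to-PASI-response curve inconsistent with the non-responder handling of the same PASI thresholds

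*Protocol*

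**What the plan says.** Time to PASI50, PASI75, PASI90 and PASI100 response "will be estimated using the Kaplan-Meier product-limit method for each treatment group" (Protocol 9.3.4). On stopping treatment the same section says: "Study participants who discontinue IMP prior to achieving a response will be censored" at their last PASI assessment, limited to assessments up to the date of stopping. SAP 5.5.3 has the same rule: "prior to achieving a response will be censored at the date of the last observed PASI assessment on" or before discontinuation. The outputs are a curve per arm and a median with its 95% CI. No between-arm test is planned.

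Elsewhere the plan handles the same event differently:
- Protocol 9.3.2 justifies the composite strategy for the co-primary endpoints by stating that "discontinuation of IMP for any reason is considered to be indicative of an ineffective response to the IMP".
- Protocol 9.3.3 extends this to the binary secondary endpoints: "the estimand structure as specified for the primary analysis will be implemented".
- For tertiary responder variables, which include PASI75, PASI90 and PASI100 over time, Protocol 9.3.4 says "nonresponder imputation (NRI) and observed case results will be displayed". SAP 5.5.1 sets data after the intercurrent event to non-response.

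Neither document defines an estimand for time to response or explains why its handling differs.

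**The concern.** Kaplan-Meier censoring is harmless when a censored participant has the same later chance of the event as those still at risk. Here the censored participants have stopped treatment, and the protocol regards stopping as a sign that treatment was not working. The method passes their share of the curve to those who stay, many of whom respond on bimekizumab.

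A reader of the study report would then see two summaries of, say, PASI90 that treat the same participants in opposite ways: failures in the response-by-visit tables, and people still expected to respond in the time-to-response curve. Speed of response is a stated objective of the study (through PASI75 at Week 4), so these curves are likely to be quoted in support of it. With 30 and 15 participants, one or two people move the curve visibly.

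**Working it through.** 1. **The plan's own figure.** No figure is given for time to response. The only design figure is 95% power for PASI90 at Week 16 (Protocol 9.8, SAP 3), from 21/30 against 2/15. Check, with continuity correction:
   - pooled proportion 23/45 = 0.511; null SE = √(0.511 × 0.489 × (1/30 + 1/15)) = 0.158
   - alternative SE = √(0.7 × 0.3/30 + 0.133 × 0.867/15) = 0.121
   - corrected difference = 0.567 − 0.5 × (1/30 + 1/15) = 0.517
   - power = Φ((0.517 − 1.96 × 0.158)/0.121) = Φ(1.71) ≈ 95.6%

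   The stated 95% reproduces and is not in dispute. The same 21/30 and 2/15 are used below.

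2. **Assumptions not in the documents.** Let k be the number of non-responding discontinuers. The 21 and 2 responders are treated as the participants who ever respond. Bimekizumab responses first occur in 1, 6, 7, 4 and 3 participants at Weeks 2, 4, 8, 12 and 16. Placebo responses come after Week 4. Visits fall exactly on schedule, and someone censored at a visit leaves after that visit's responses.

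3. **Formula, bimekizumab, discontinuers last seen at Week 4.** Before Week 8 the survival estimate is 23/30, with 23 − k at risk. The later factors are (16 − k)/(23 − k), (12 − k)/(16 − k) and (9 − k)/(12 − k), so

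   S(Week 16) = (23/30) × (9 − k)/(23 − k).

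   If last seen at Week 8, S = (16/30) × (9 − k)/(16 − k). If they leave before any response, the curve ends at 21/(30 − k), which is the upper bound.

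   | k | Proportion responding | 1 − KM, last seen W4 | 1 − KM, last seen W8 | Bound 21/(30 − k) |
   |---|---|---|---|---|
   | 0 | 70.0% | 70.0% | 70.0% | 70.0% |
   | 1 | 70.0% | 72.1% | 71.6% | 72.4% |
   | 2 | 70.0% | 74.4% | 73.3% | 75.0% |
   | 3 | 70.0% | 77.0% | 75.4% | 77.8% |

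   At 26/30 (about 87%, inside the 85% to 90% quoted for the global program), the bound with k = 3 is 26/27 = 96.3%, an excess of up to 9.6 points.

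4. **Placebo, last seen at Week 4.** 1 − KM = 2/(15 − k), which is 14.3%, 15.4%, 16.7% and 18.2% for k = 1 to 4, against 13.3%. The excess is 1.0, 2.1, 3.3 and 4.8 points.

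5. **Between-arm gap.** With 1 discontinuer on bimekizumab and 4 on placebo, all at Week 4, the gap is 72.1 − 18.2 = 53.9 points, against 70.0 − 13.3 = 56.7 from the responder proportions. It shrinks.

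6. **Median, bimekizumab.** After Week 8, S = (23/30) × (16 − k)/(23 − k), which is 0.533, 0.523, 0.511 and 0.498 for k = 0 to 3. The median stays at Week 12 for k = 1 or 2 and moves to Week 8 for k = 3. The margin at k = 2 is thin, so another response timing could move it.

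7. **Which end day works.** On the SAP's day count, Week 16 is Day 113, and the ±3-day window allows Days 110 to 116. Take k = 3 and hold the discontinuers only to Day 113. If the three Week 16 responses fall on Days 114 to 116 and the six completing non-responders are seen no earlier, S = (12/30) × (6/9) and the curve ends at 73.3%. If three of those six are also seen by Day 113, S = (12/30) × (3/6) and it ends at 80.0%. With all nine non-responders held past Day 116, S = (12/30) × (9/12) = 9/30 and it ends at 70.0%, exactly the responder proportion.

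**The case against.** The case for the plan has force on several points.

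- A reader might infer that the plan breaks its own rule that stopping treatment is failure. It does not. That sentence justifies the co-primary strategy and is carried to binary endpoints. SAP 5.1.1.7 treats tertiary data after the intercurrent event as missing, to be handled as section 5.5 says, and 5.5.3 says to censor. Protocol and SAP agree. The plan also varies its strategy elsewhere: percent change in BSA uses a hypothetical strategy for the same event.
- A reader might infer that every other responder analysis counts discontinuers as failures. Observed-case analyses do not (SAP 5.3.3, 5.4.1.3 and 5.5.1). The statement is true only of the main analyses.
- A reader might infer that the excess favors bimekizumab. Both arms are inflated, and step 5 shows the gap can narrow.
- Non-responder figures of PASI response by visit are already planned (SAP 5.5.1), so the failure-based view will be on the page.
- The median, the only numerical summary named for this analysis, often does not move.
- The endpoint is tertiary, descriptive and untested.

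All of this stands, and it limits the point to an unexplained inconsistency. It does not remove it. The by-visit figures are not cumulative, so they do not correct the Kaplan-Meier curve, and a reader has no statement of which question that curve answers.

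**Conclusion.** The point holds as an inconsistent choice of strategy for one tertiary analysis. Censoring before response assumes later response at the rate of those who stay, which does not fit the protocol's own reasoning or the handling of PASI75, PASI90 and PASI100 over time.

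In either arm, pre-response discontinuation can only push the final value of the curve up. At 21/30 the excess is about 2, 4 and 7 points for 1, 2 and 3 discontinuers last seen at Week 4, and about 2, 3 and 5 points if last seen at Week 8. At 2/15 on placebo it is about 1 to 3 points for 1 to 3 discontinuers. These sizes rest on assumed counts and response timing, because the documents give no discontinuation rate; with none before response, this effect is zero. Calling it bias also presumes that the composite reading is the one wanted.

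The documents do not support saying that the plan contradicts a rule governing this endpoint, that the treatment comparison is tilted toward bimekizumab, or that the main result is at risk. The co-primary tests and the power are untouched. This is a small improvement worth making.

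**What to change.** Amend Protocol 9.3.4 and SAP 5.5.3 as follows.

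- Make the main time-to-response curve a cumulative incidence in which stopping IMP before response counts as non-response. Either treat it as a competing event or keep the participant in the risk set.
- Place all non-responders, discontinuers and completers alike, at one common end day after the last permitted Week 16 date, that is after Day 116; or run the analysis on nominal visit weeks. Day 113 is not late enough (step 7). The competing-event version needs the common day too, because completers censored at an early Week 16 visit still leave before later responses.
- Keep the current censoring as a sensitivity analysis, labeled with the question it answers.
- In SAP 5.5.3, change 70 to 75 in the heading and in the list of xx values. This is clerical; the body text already says PASI75.

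The cost is wording in two documents, slightly more programming, and a slightly lower curve in any arm with discontinuers.

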9.4 Planned safety and other analyses

Safety variables will be analyzed for all study participants in the SS.

9.4.1 Safety analyses

9.4.1.1 AEs

Adverse events will be coded according to the Medical Dictionary for Regulatory Activities (MedDRA v19.0). Treatment-emergent AEs are defined as those AEs that have a start date on or following the first dose of IMP.

The frequency of all TEAEs will be presented for each treatment group separately by system organ class, high level term, and preferred term. The data will be displayed as number of study participants experiencing the TEAE, percentage of study participants, and number of TEAEs. Additional tables will summarize serious TEAEs, TEAEs leading to discontinuation, TEAEs by severity, and TEAEs categorized as safety topics of interest and AESIs. Definitions for categorizing TEAEs as safety topics of interest and AESIs will be provided in the SAP.

Further details of TEAE summaries will be provided in the SAP.

9.4.1.2 Vital signs

Vital signs will be summarized by visit. Absolute values and change from Baseline in systolic and diastolic BP and pulse rate will be presented descriptively by visit for each treatment group.

Markedly abnormal vital signs will be summarized. Definitions of markedly abnormal vital signs will be given in the SAP.

9.4.1.3 Hematology/biochemistry

Treatment-emergent markedly abnormal (TEMA) laboratory values are defined as those that have an assessment date on or following first dose of IMP.

Laboratory assessments will be analyzed by visit. Absolute values and change from Baseline in each laboratory parameter will be presented descriptively for each treatment group. The incidence rate of TEMA laboratory values at the parameter level will also be presented descriptively for each treatment group. Definitions for markedly abnormal laboratory values will be provided in the SAP.

9.4.1.4 Physical examination

Clinically significant changes from Baseline in physical examination findings will be reported as AEs and included in the TEAE summarization described in Section 9.4.1.1.

9.4.1.5 ECG

Changes from Baseline in ECG parameters will be summarized by treatment group. ECG outliers will be summarized as defined in the SAP.

